6.3.1.4. MA-LRTIs Due to RSV Occurring 361 Days to 730 Days After Birth

The interval of interest for this analysis is 361 to 730 days after birth. All attributes (including analysis methodology and reporting results) for this endpoint will be similar to those stated in Section 6.3.1.2.

6.3.1.5. Severe MA-LRTIs Due to RSV (as Confirmed by the EAC) Occurring 181 Days to 730 Days After Birth

The interval of interest for this analysis is 181 to 730 days after birth. All attributes (including analysis methodology and reporting results) for this endpoint will be similar to those stated in Section 6.3.1.2.

6.3.1.6. Hospitalization Due to RSV (as Confirmed by the EAC) Occurring 181 to 730 Days After Birth

The interval of interest for this analysis is 181 to 730 days after birth. All attributes (including analysis methodology and reporting results) for this endpoint will be similar to those stated in Section 6.3.1.2.

6.3.1.7. MA-LRTIs Due to Any Cause Occurring 181 to 730 Days After Birth

The interval of interest for this analysis is 181 to 730 days after birth. All attributes (including analysis methodology and reporting results) for this endpoint will be similar to those stated in [Section 6.3.1.2](#).

6.3.1.8. RSV Subgroup A– and Subgroup B–Specific MA-LRTI (as Confirmed by the EAC) Occurring Within 180 Days After Birth

- Analysis set: Evaluable efficacy – infant ([Section 4](#)).
- Analysis methodology: VE will be analyzed using a conditional exact test based on the binomial distribution of the number of disease cases in the RSV vaccine group, given the total number of cases in both groups. Events that happen after the infant received palivizumab or another monoclonal antibody targeting RSV or after he/she had transfusions of more than 20 mL/kg of any blood products at ≤ 180 days of age will be excluded.
- For each group, the number (n), percentage, and 95% CI of RSV subgroup A– and subgroup B–specific MA-LRTI cases occurring within 180 days (as confirmed by the EAC or RSV-positive severe MA-LRTI adjudicated cases) will be presented for each group (only RSV positivity from the Pfizer central laboratory will be considered; RSV-positive results from local tests that have no corresponding VRD-confirmed positive result will be considered to be in an RSV subgroup of “indeterminate”).
- VE in the RSV vaccine group compared to the placebo group along with the 95% CI will be presented.

6.3.1.9. Positivity for Non-RSV Pathogens Obtained at MA-RTI Visits Occurring Within 180 Days After Birth

- Analysis set: Evaluable efficacy – infant ([Section 4](#)).
- Analysis methodology: Descriptive summary statistics.
- For each group, the number and percentage of participants with positive non-RSV respiratory pathogen results (from local tests) will be presented.
- For each group, the number and proportion of participants with positive non-RSV respiratory pathogens (from nasal swabs collected at an RTI study visit and tested by the Pfizer central laboratory for a panel of target pathogens, including SARS-CoV-2) will be presented. In addition, a separate analysis using RSV-positive adjudicated MA-LRTI cases might be presented separately.

6.3.1.10. RSV A and RSV B Serum Neutralizing Titers Measured at Birth

- Analysis set: Evaluable immunogenicity – infant (Section 4).
- Analysis methodology: Descriptive summary statistics. Results obtained from out-of-window blood draws will also be removed. Missing serology results will not be imputed, as MCAR is assumed. Only samples tested by the Pfizer central laboratory will be considered for this analysis.
- GMTs of the RSV A and RSV B serum neutralizing titers will be descriptively summarized for each vaccine group, along with associated 2-sided 95% CIs.
- GMTs of the combined RSV A/B serum neutralizing titer will be descriptively summarized for each vaccine group, along with associated 2-sided 95% CIs.
- GMRs of the RSV vaccine group to the placebo group for the RSV A and RSV B serum neutralizing titers will be calculated, along with associated 2-sided 95% CIs.
- GMR of the RSV vaccine group to the placebo group for the combined RSV A/B serum neutralizing titers will be calculated, along with associated 2-sided 95% CIs.
- Geometric means of the placental transfer ratio and associated 2-sided 95% CIs will be provided for RSV A, RSV B, and combined RSV A/B serum neutralizing titers. For each mother-infant dyad, the transfer ratio will be calculated as the ratio of the infant's RSV serum neutralizing titer at birth to the mother's RSV serum neutralizing titer at delivery. Group geometric means and CIs are calculated in the same way as for similar endpoints using the fold rise calculated above.
- A correlation scatterplot will be generated, with the infant blood titer on the x-axis and maternal titer on the y-axis.

6.3.1.11. Healthcare Resource Utilization

6.3.1.11.1. Main Analysis

- Analysis set: Safety population – infant (Section 4).
- Analysis methodology: Univariate summaries of healthcare resource utilization variables will be compared between the RSVpreF and placebo groups.
- For categorical variables (type and setting of medical visit, mechanical ventilation [yes/no], respiratory diagnostic procedures [yes/no], IV fluids [yes/no], selected respiratory medications [yes/no], antibiotic use [yes/no]), the number, percent, odds ratios, and associated two-sided 95% CI will be presented.

- For continuous variables (the number of medical visits, length of hospital stay, total number of mechanical ventilation episodes, total number of hours/days on mechanical ventilation, total number of prescriptions, total number of antibiotic use days), the mean, SD, difference in means, and associated 2-sided 95% CI will be presented.

6.3.1.11.2. Supplementary Analysis

Some healthcare utilization variables will also be compared between RSVpreF and placebo groups using only RSV-positive MA-LRTI cases.

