2.1.3. Exploratory Objectives

2.1.3.1. Exploratory Objectives – Infant Participants

- To evaluate the efficacy of RSVpreF in reducing the incidence of MA-RTI due to RSV.
- To evaluate the efficacy of RSVpreF in reducing the incidence of MA-RTI.
- To evaluate the efficacy of RSVpreF in reducing the incidence of MA-LRTI due to RSV in infants after 12 months of age.
- To evaluate the efficacy of RSVpreF in reducing the incidence of severe MA-LRTI due to RSV in infants after 6 months of age.
- To evaluate the efficacy of RSVpreF in reducing the incidence of hospitalization due to RSV in infants after 6 months of age.
- To evaluate the efficacy of RSVpreF in reducing the incidence of all-cause MA-LRTI in infants after 6 months of age.

- To evaluate the efficacy of RSVpreF in reducing the incidence of MA-LRTIs due to RSV A and the incidence of MA-LRTIs due to RSV B.
- To describe the non-RSV infectious etiology of MA-RTI in the study population.
- To evaluate RSV serum neutralizing titers elicited by RSVpreF and transferred transplacentally.
- To assess the impact of RSVpreF on RSV illness based on socioeconomic factors.
- To assess the effect of RSVpreF on healthcare utilization.
- To describe the efficacy of RSVpreF in reducing the incidence of MA-RTI, MA-LRTI, and severe MA-LRTI in premature infants <37 weeks of age.

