2.2. Study Design

This is a Phase 3, multicenter, randomized, double-blinded, placebo-controlled study to assess the efficacy, safety, and immunogenicity of bivalent RSVpreF or placebo (1:1 randomization) in infants born to healthy women vaccinated during pregnancy, and the safety and immunogenicity in the pregnant women. This will be a global study, including sites in both the northern and southern hemispheres, and it will span multiple RSV seasons.

This is an event-driven study with a target of 124 adjudicated (primary-endpoint) cases of MA-LRTI due to RSV (meeting the case definition in the per-protocol infant population described in [Section 9.2 of the protocol](#)). Vaccination of maternal participants will occur at a time of year such that the infant is likely to be exposed to seasonal RSV during the first 6 months of life. It was anticipated that approximately 6900 mother-infant pairs would be needed to accumulate 124 per-protocol cases prior to the global COVID-19 pandemic. With the variable RSV season, the sample size may need to be increased and enrollment could go up to 10,000 maternal participants based on the number of RSV cases.

Study-eligible pregnant women will be randomized in a 1:1 ratio to receive a single dose RSVpreF or placebo. The dose of RSV prefusion F antigen in RSVpreF for this study will be 120 µg (60 µg A and 60 µg B).

Assessments for mothers will include parameters to allow descriptions of safety, tolerability, and immunogenicity of the vaccine in maternal participants.

For all infant participants, data will be collected for any medically attended respiratory illness to assess for cases of LRTI due to RSV (efficacy endpoint). Additionally, throughout the study all respiratory illnesses, SAEs, and NDCMCs reported will be assessed in this population. Infant participants enrolled during the first year of the study will be followed up for 24 months after birth, to include longer-term RTI surveillance and safety oversight to address safety and the possibility of conferred enhanced protection (antibody persistence) during a second RSV season. All other infants will be followed up for 12 months after birth. All MA-RTIs meeting the protocol definition for a potential study endpoint will be adjudicated by an independent EAC. In addition, this study will use an E-DMC to monitor vaccine safety and efficacy and study futility.

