3.6. Health Economics

3.6.1. Healthcare Resource Utilization: Infant Participants

Details of healthcare resource utilization for all infants will be assessed at each MA-RTI visit from 72 hours after birth through the last study visit (730 days after birth). The variables collected will include the following: number, type (eg, respiratory, RAD/asthma/wheezing), and setting (eg, outpatient, urgent care, emergency room, hospitalization, ICU) of healthcare visits, length of hospital stay, requirement for mechanical ventilation (yes/no, total number of mechanical ventilation episodes, total number of hours/days on mechanical ventilation), requirement for respiratory diagnostic procedures (eg, chest radiograph, supplemental oxygen, pulse oximetry), requirement for IV fluids, requirement for prescriptions (eg, total number of prescriptions, selected respiratory medications [eg, bronchodilators, corticosteroid therapy, racemic epinephrine]), and antibiotic use (eg, total number of prescriptions, number of antibiotic use days).

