4. ANALYSIS SETS (POPULATIONS FOR ANALYSIS)

Data for all participants will be assessed to determine if participants meet the criteria for inclusion in each analysis population prior to unblinding and releasing the database and classifications will be documented per standard operating procedures.

Population	Description
Enrolled	All participants who sign the informed consent document.
Randomly assigned to investigational product	All maternal participants who are assigned a randomization number in the IRT system.
Evaluable efficacy – infant (per-protocol)	All infant participants who are born to maternal participants who did not have major protocol deviations prior to the delivery and who received the investigational product to which they were randomized at least 14 days prior to delivery, are eligible, and have no major protocol deviations.
ITT efficacy – infant	All infant participants who are born to vaccinated maternal participants.
Evaluable immunogenicity – infant	All infant participants who are born to maternal participants who did not have major protocol deviations prior to the delivery and who received the investigational product to which they were randomized, are eligible, have blood drawn for assay testing within the specified time frame, ^a have valid and determinate assay results for the proposed analysis, and have no major protocol deviations.
Evaluable immunogenicity – maternal	All maternal participants who are eligible, receive the investigational product to which they were randomized, have blood drawn for assay testing within the specified time frame, ^b have valid and determinate assay results for the proposed analysis, and have no major protocol deviations.
ITT immunogenicity – infant	All infant participants who are born to vaccinated maternal participants and have at least 1 valid and determinate assay result for the proposed analysis.
ITT immunogenicity – maternal	All randomized maternal participants who receive investigational product and have at least 1 valid and determinate assay result for the proposed analysis.
Safety – infant	All infant participants who are born to vaccinated maternal participants.
Safety – maternal	All randomized maternal participants who receive investigational product.

- a. A cord blood sample must be obtained on the day of birth. If cord blood is unavailable, a venous blood sample may be collected from the infant preferably within 24 hours but up to 7 days after birth.

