5.3.3. Efficacy Data

Cases that qualify as MA-LRTI events based on clinical signs and symptoms but do not have a valid RSV swab result will be identified. Sensitivity analyses of the primary endpoints will be done under various assumptions about the missing swab results. In each scenario, cases with imputed positive RSV results will be added to the confirmed RSV-positive cases and vaccine efficacy in the augmented set of cases analyzed.

Based on a blinded review of swab results at the end of February 2022, approximately 22% of all swabs from MA-LRTI events with valid central lab results cases proved to be RSV-positive. Thus, a minority of the missing results are expected to be truly RSV-positive, and imputation scenarios will include:

- Missing swab results are assumed to be positive in the same proportion (by vaccine group) as the nonmissing swab results in MA-LRTI events (missing-at-random assumption).
- For the vaccine group, missing swab results are assumed to be positive in higher proportions than the nonmissing swab results in MA-LRTI events, while in the placebo group missing swab results are assumed to be positive in the same proportion as the nonmissing swab results in MA-LRTI events (missing-not-at-random assumption). A range of higher vaccine group positivity rates will be assumed.

Multiple imputations will be performed to randomly assign missing swab results. SAS PROC MI will be used to generate 500 imputed data sets for each scenario. Mean and median VE across imputations, and the proportion of imputations with VE lower bound >20% will be reported.

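### The RSV-specific healthcare-utilization comparison in SAP 6.3.1.11.2 is restricted to RSV cases, so randomization does not protect it and averted illness drops out

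*SAP*

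**What the plan says.** The exploratory objective in SAP 2.1.3.1 is "To assess the effect of RSVpreF on healthcare utilization". Two analyses serve it.

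- **Main analysis (6.3.1.11.1).** In the infant safety population, "Univariate summaries of healthcare resource utilization variables will be compared between the RSVpreF and placebo groups". Categorical variables get odds ratios and continuous variables get differences in means, each with a 95% CI. Section 4 defines that population as "All infant participants who are born to vaccinated maternal participants". Section 3.6.1 says "Details of healthcare resource utilization for all infants will be assessed at each MA-RTI visit", from 72 hours after birth to the last study visit. This comparison therefore covers all infants and all causes.
- **Supplementary analysis (6.3.1.11.2).** The whole text is: "Some healthcare utilization variables will also be compared between RSVpreF and placebo groups using only RSV-positive MA-LRTI cases". It names no analysis set, denominator or statistic, does not say how infants without an RSV episode enter, and does not say that the result describes breakthrough illness only.

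Some RSV-specific outcomes that bear on utilization are analysed in the evaluable efficacy infant set: hospitalization due to RSV (6.2.1.1.1, and 6.3.1.6 for days 181 to 730), RSV hospitalization with ICU admission (6.2.1.1.2), severe MA-LRTI due to RSV (6.1.1.2.1, with ventilation and ICU stay among the qualifying criteria in Table 8), and RSV-positive MA-RTI (6.3.1.1 and 6.3.1.2).

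**The concern.** RSV-positive MA-LRTI is the first primary efficacy endpoint. Restricting a between-group comparison to infants who reached it conditions on something that happened after randomization and that the vaccine is designed to change. Two consequences follow.

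- Vaccine-group cases are those the vaccine failed to prevent. They can differ from placebo cases in severity, age or frailty, so a difference between the two sets is not an effect of vaccination.
- A prevented case contributes to neither numerator nor denominator. The main way a vaccine saves healthcare resources is by preventing cases, and that part of the effect is removed.

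This is the only RSV-specific comparison the SAP plans for length of stay, ventilation duration, IV fluids, prescriptions, antibiotic days and number of visits. A null or adverse table could be read as no benefit on these variables, and a favourable one as a randomized effect. Neither reading would be justified.

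**Working it through.** The SAP gives no figure for this analysis, so there is none to reproduce. The check compares what a per-case contrast and a per-infant contrast would show from the same events.

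**Inputs from the SAP.** Section 2.2: "approximately 6900 mother-infant pairs would be needed to accumulate 124 per-protocol cases", and "Study-eligible pregnant women will be randomized in a 1:1 ratio to receive a single dose RSVpreF or placebo", hence 6900 / 2 = 3450 infants per group. Section 7.2: design efficacy 60%.

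**Assumptions, not SAP figures.** 30% of placebo cases are resource-heavy. A light case uses 1 unit of resource and a heavy case 5.

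**Cases by group.** Placebo = 124 / (1 + 0.40) = 88.6; vaccine = 124 − 88.6 = 35.4. Placebo light = 0.70 × 88.6 = 62.0; placebo heavy = 0.30 × 88.6 = 26.6.

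**Placebo utilization.** Per case = 0.70 × 1 + 0.30 × 5 = 2.20. Per 100 infants = 100 × 88.6 × 2.20 / 3450 = 5.65.

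**Vaccine utilization.** Light cases = 62.0 × (1 − VE light); heavy cases = 26.6 × (1 − VE heavy). Per case = (light + 5 × heavy) / (light + heavy). Per 100 infants = 100 × (light + 5 × heavy) / 3450. Every row keeps overall efficacy at 60%.

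| VE light / heavy | Vaccine light / heavy cases | Per case, placebo vs vaccine | Per 100 infants, placebo vs vaccine | Fall per infant | Case-only odds ratio for heavy illness |
|---|---|---|---|---|---|
| 60% / 60% | 24.8 / 10.6 | 2.20 vs 2.20 | 5.65 vs 2.26 | 60% | 1.0 |
| 70% / 36.7% | 18.6 / 16.8 | 2.20 vs 2.90 | 5.65 vs 2.98 | 47% | 2.1 |
| 65% / 48.3% | 21.7 / 13.7 | 2.20 vs 2.55 | 5.65 vs 2.62 | 54% | 1.5 |
| 50% / 83.3% | 31.0 / 4.4 | 2.20 vs 1.50 | 5.65 vs 1.54 | 73% | 0.33 |

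The pattern follows from an identity: the per-case ratio equals the per-infant ratio divided by the ratio of case counts, here 35.4 / 88.6 = 0.40. In row 1, 0.40 / 0.40 = 1. In row 4, 0.273 / 0.40 = 0.68, which is 1.50 / 2.20. With equal efficacy at every severity the per-case contrast is null whatever the size of the efficacy, the resource weights or the number of infants. Where efficacy is higher against heavy illness it has the right sign but understates the benefit (a 32% fall per case against 73% per infant). It reverses only where efficacy is lower against heavy illness.

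**Precision of a reversed result.** Take 89 placebo cases, 59 not hospitalized and 30 hospitalized, with assumed efficacy of 70% and 50%. The vaccine group has 59 × 0.30 ≈ 18 and 30 × 0.50 = 15. Hospitalization per infant halves, while the case-only odds ratio is (15/18) / (30/59) = 1.64. Its log standard error is √(1/15 + 1/18 + 1/30 + 1/59) = 0.415, giving a Wald 95% CI of about 0.73 to 3.7.

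**The case against.** There are five serious counter-arguments.

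- **The objective is all-cause, and the main analysis answers it.** This stands. The objective does not say RSV-related utilization. Section 6.3.1.11.1 keeps the randomized groups and counts prevented illness. A reader might infer that the plan as a whole hides the vaccine's effect on utilization; it does not.
- **RSV-specific outcomes are compared in all evaluable infants elsewhere.** This stands for hospitalization, ICU admission, severe MA-LRTI and the occurrence of RSV-positive MA-RTI. It does not extend to the quantities listed under the concern, so the gap is narrower than all RSV-related utilization.
- **The denominator is not stated.** This stands in part. Section 6.2.1.1.2 uses similar wording to restrict which events count while keeping the whole population, and 6.3.1.11.2 could be meant the same way. Comparing groups by using cases alone more naturally means a case denominator. If all infants were intended, the sentence must say so.
- **Reversal is speculative.** This stands. A reader might infer that the table will show harm. That requires lower efficacy against resource-heavy illness, which no section supports, and the illustrative odds ratio has an interval that includes 1. The null result under equal efficacy needs no such assumption.
- **Dilution of the main analysis cannot be sized.** This stands. Section 5.3.3 reports that "approximately 22% of all swabs from MA-LRTI events with valid central lab results cases proved to be RSV-positive", and a reader might turn this into a dilution factor for the main analysis. The figure describes tested MA-LRTI swabs, whereas the main analysis covers all MA-RTI visits through the last study visit. The SAP gives no RSV share for that set.

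**Conclusion.** The point holds as a limited one. Read naturally, 6.3.1.11.2 conditions on the primary efficacy outcome, and its between-group contrast cannot be read as an effect of RSVpreF on utilization. With equal efficacy at every severity it shows no difference while utilization per infant falls by the full efficacy, 60% at the design value. In the unequal scenarios the per-case ratio ran from 0.68 to 1.32 (1.50 / 2.20 to 2.90 / 2.20) while utilization per infant fell by 47% to 73%. Those ranges rest on the assumed severity mix and resource weights; the null result under equal efficacy does not.

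The consequence is confined to RSV-attributable length of stay, ventilation duration, IV fluids, prescriptions, antibiotic days and number of visits, in a supplementary analysis of an exploratory endpoint. No primary or secondary inference is affected. The change is worth making because it is cheap and the data are already being collected.

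**What to change.** Replace the sentence in 6.3.1.11.2 with the following elements.

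1. Utilization arising from RSV-positive MA-LRTI episodes, summarized per infant over the full Safety – infant set by randomized group, with infants without such an episode counted as zero. Report the percentage of infants with each resource and, for the quantitative variables, the mean per infant with the difference and 95% CI.
2. A follow-up window common to all infants, for example through 360 days, or rates per unit of follow-up time. Section 2.2 plans 12 months of follow-up for some infants and 24 for others, so a zero must mean the same length of observation.
3. A count by group of MA-LRTI episodes without a valid swab, since these would otherwise enter as zero RSV utilization. Section 5.3.3 already identifies them.
4. Case-only figures kept as a description of breakthrough illness, without between-group odds ratios or differences.

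The cost is SAP wording and a changed denominator in a few tables, with no new data. The drawback is that per-infant means will be small, because most infants contribute zero.
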